Ewald & Wasserman (E&W) will conduct the Aim 3 cluster randomized crossover trial at up to 32 hookah cafés (1 pilot and 31 trial cafés) in Atlanta, GA. This trial will be conducted entirely in the field at the participating cafés. Hookah cafés will be recruited to partner with the research team, which involves allowing participants to be recruited and data collection to occur outside the café prior to café entry and after café exit on at least two data collection periods (across the two trial arms). Cafés must also agree to allow the research team to post health warnings about hookah smoking in the cafés on some of the days of data collection. E&W will be responsible for the recruitment of hookah cafés, hiring of field staff, training of field staff on data collection procedures (in conjunction with the Wake Forest study team), and implementing all data collection procedures. Data collection will involve field research at the hookah cafés. Field staff will approach potential participants before they enter the café to assess interest in the study and eligibility. For those eligible, field staff will complete the consenting process, administer a brief survey on tablet computers, collect expired carbon monoxide breath measurements, and distribute incentives at two time points: before participants enter the café and after they exit. Additionally, field staff will debrief participants at the end of the study. E&W will also be responsible for all participant payments. Finally, E&W will be responsible for printing, implementing, and removing the warning signs at waterpipe cafés.

Methods and Measures

Design

The design of the study is a cluster randomized crossover trial, where the hookah café is the cluster and randomization is at the cluster level. Each hookah café will serve as its own control and will be used for data collection for both study arms: (1) intervention, and (2) control. Each café will start in the no warning control arm to avoid the potential for contamination, since customers may visit the same café on multiple days. In the intervention arm, cafés will display one of four text warnings. In the intervention arm, warning messages will be displayed at various agreed-upon locations in the café, such as on hookah pipes, tables, countertops, walls, and menus. The goal is to maximize the potential for customers to be exposed to warnings.

Setting

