Data collection will occur outside hookah cafés in the Atlanta, GA metro area. Atlanta was chosen as the study site because Georgia's weak smoke-free air law allows smoking in bars and restaurants, including hookah cafés. There are over 100 hookah cafés in the Atlanta metropolitan area and Atlanta is home to 57 colleges and universities. The number of cafés and young adults, and the weak smoke-free air laws make Atlanta the ideal location for this study. We will partner with one pilot café and up to 31 additional cafés to allow study activities, including collecting data with customers before café entry and after café exit, and display of study-produced health warnings about hookah smoking during the times when data collection is occurring. Participants will complete data collection outside of the café at two time points, before entry into the café and after exit from the café.

Subject Selection Criteria

Participants will be those planning to enter a hookah café where the study is being conducted. We aim to have 15 participants complete Time 1 (before café entry) and Time 2 (after café exit) data collection at each café for each arm. In order to account for attrition between time points, we will enroll up to 30 participants at each café during each data collection period. We will schedule data collection periods for when the café is most busy, based on information provided by the café manager or owner.

Inclusion Criteria

- Planning to enter the hookah café where study is being conducted
- Age 18 or older
- English speakers
- Planning to smoke hookah inside
- Planning not to smoke cigarettes, cigars, cigarillos, or marijuana while at the hookah café
- Had not previously entered the café earlier in the day on the same day/night as data collection
- Has not been approached to participate in the study at another café or another day/night at the current café
- Are not employees of the business
- Have capacity to participate as determined by the staff member conducting eligibility screening

Exclusion Criteria

- Not planning to enter the hookah café where the study is being conducted
- Age 17 or under
- Non-English speakers
- Not planning to smoke hookah in the café
- Planning to smoke cigarettes, cigars, or marijuana while at the hookah café
- Are employees of the business
- Has not been approached to participate in the study previously
- Had previously entered the café on the same day/night as data collection

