Data collectors will also make a determination, based on their interaction with the participant, of the participant's capacity to participate in the study. If they determine that the person does not have capacity, they will mark this on the Eligibility Form and the participant will be Not Eligible. If they determine that the person does have capacity, they will mark the participant such on the Eligibility Form and will continue with the Consent process. Determination of capacity to participate will be based on whether people can adequately answer the eligibility screening questions. Eligible participants will be read the consent information by a data collector prior to enrollment and provide verbal consent. A printed consent document will be available for participants if they ask to see it.

After completing the consent process, participants will be given a wristband with their participant ID. Then, they will complete a brief survey about their hookah use behaviors, demographics, and recent use of other combustible products. They will enter their email into a Qualtrics link managed by Ewald & Wasserman to receive their first (\$25) electronic gift card; this is not stored with study data, although it is linked to PID. Next, participants will provide up to two samples of expired carbon monoxide (eCO) by blowing into a carbon monoxide (CO) monitor. This non-invasive process involves taking a deep breath, holding it for 15 seconds, and then exhaling into a sterile tube until the lungs are completely empty. Expired CO is a well-established measure of tobacco smoke exposure. Participants will then be able to enter the café as planned. All participants will be asked to return to the data collectors after exiting the café to complete the follow-up measures. If the data collection period is scheduled to end before the café closes, data collectors will instruct the participants to come outside for Time 2 measures before the data collection period will end. Upon exiting the café, participants will complete a similar brief survey, provide their email again for their second (\$50) compensation, and provide up to two new samples of eCO, using the same procedure as described above. Participants will be debriefed on the purpose of the study and the CO measure. The debrief form will also have resources for more information about CO and health harms of hookah smoking, and contact information for the study PI, the Wake Forest IRB, and E&W for assistance with compensation.

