The participant incentives are not intended to be an enticement to smoke hookah within the café, but rather as compensation for time needed to complete the surveys and eCO monitoring, which we anticipate will take up to 20 minutes at each time point. Participants will only be eligible if they indicate they are planning to smoke hookah in the café. We will not recruit people to come to the café, but rather recruit café customers to participants in the study. Participants will be instructed to behave as they normally would in the café. The incentive will not be able to be used in the café.

Figure 1. Table Sign

Pilot/Soft Launch

We will conduct a pilot/soft launch with a single hookah café to assess feasibility of the protocol and to make changes, if required, before conducting the full trial. Any changes to protocol and/or measures will be submitted as amendments before conducting the remainder of the trial. If no changes are made as a result of the soft launch, this café will be included in the final study sample. If significant changes are made as a result of the soft launch, we will conduct the study with up to 25 additional cafés and the data from the soft launch café will not be included in the final dataset. We will implement both text-only and pictorial warnings on different nights at the pilot café to fully test the two versions of the intervention signs, in addition to the control arm.

Outcome Measure(s)

Primary Outcome

Change in Expired Carbon Monoxide from baseline to follow-up. We will use eCO, an objective, biological marker of waterpipe tobacco consumption. There is a linear relationship between waterpipe tobacco smoking intensity and carboxyhemoglobin concentration, and eCO is strongly correlated with several topography measures of waterpipe smoking. Carbon monoxide has a half-life of 3-4 hours and is influenced by other forms of combustible tobacco; therefore, the primary outcome will be the change in eCO from before entry to after café exit, known as eCO boost. We will also record the percentage of carboxyhemoglobin concentration measured by the CO monitor.

Secondary Outcome(s)

None

Other Outcomes

Behavioral intentions. Participants will be asked at Time 2 three items assessing their expected hookah smoking within the next month. Items will be averaged to create a composite score of intent to continue the behavior within the next month.

1. How interested are you in smoking tobacco in a hookah in the next month?

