of individuals within study arm within cafés. We let eCO_{ijk} represent the outcome measurement for individual k within study arm j within cluster (café) I , assumed continuous and normally distributed. The model will include a fixed effect for study arm (intervention or control) and random cluster and cluster-arm effects. Models will adjust for individual-level sociodemographics and tobacco use at baseline. In secondary analyses, we will examine the impact of sociability of waterpipe behavior by adjusting models for the number of people with whom the individual is smoking in the café. Secondary analyses will examine the impact of text versus pictorial warnings. These hierarchical models will be fit using PROC MIXED in SAS. Because the intervention effect is estimated within clusters, it is also adequate to model fixed cluster effects but retain random cluster-arm effects. Turner (2007) demonstrated through simulation that these two models perform similarly with 18 clusters with slight differences depending on the degree of correlation. We will examine both approaches as a sensitivity analysis.²² Using the same HLM modeling approach, we will perform analyses on secondary outcomes shown in Table 5.

Human Subjects Protection

Overview

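### The primary model for change in eCO does not name Time 1 eCO as a covariate or say how repeat readings are combined; prespecify both and report the model without the covariate as a sensitivity analysis

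*Combined protocol and SAP*

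**What the plan says.** Under Primary Outcome, "the primary outcome will be the change in eCO from before entry to after café exit, known as eCO boost". The reason given is that "Carbon monoxide has a half-life of 3-4 hours and is influenced by other forms of combustible tobacco".

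The Analytical Plan describes a hierarchical linear model with a fixed arm effect and random café and café-by-arm effects. On covariates it says: "Models will adjust for individual-level sociodemographics and tobacco use at baseline". The only sensitivity analysis planned for the model's form is fixed against random café effects.

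Under Data Collection, consented participants first answer questions: "they will complete a brief survey about their hookah use behaviors, demographics, and recent use of other combustible products". The breath test is a separate, later step, in which "participants will provide up to two samples of expired carbon monoxide (eCO". The same applies at Time 2. The text does not say whether the first, the mean or another reading is analysed.

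Two design features bear on this. Under Design, "Each café will start in the no warning control arm to avoid the potential for contamination". Under Inclusion Criteria, a participant "Has not been approached to participate in the study at another café or another day/night at the current café", so the two arms of a café hold different people. The criterion on other smoking, "Planning not to smoke cigarettes, cigars, cigarillos, or marijuana while at the hookah café", concerns behaviour inside the café and does not limit smoking before arrival.

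**The concern.** Analysing Time 2 minus Time 1 without Time 1 as a covariate is the same as modelling Time 2 eCO with the Time 1 coefficient fixed at 1. If part of the arrival CO has washed out by exit, that coefficient is too large, and patrons who arrive with more CO show a smaller boost whatever the signs do. Arm order is fixed and each arm recruits its own patrons, so randomisation does not balance arrival eCO between arms. A higher arrival level on warning nights would then imitate a benefit, and a lower one would hide it. The documents do not indicate which way any difference would go.

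The covariate phrase most naturally means the survey items, so the self-report adjustment may leave some arrival difference in place. With the reading rule and the baseline covariate both open, part of the primary analysis could also be settled after the data are seen.

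**Working it through.** **Inputs from the documents.** 20 cafés, 15 completers per arm per café, SD of change 30 ppm, r = 0.10 or 0.30, h = r/2, 80% power (Analytical Plan); CO half-life 3-4 hours (Primary Outcome); published boost 51.7 ppm, or 795% (Analytical Plan).

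**Assumptions.** Two-sided alpha of 0.05 (not stated, but it reproduces the plan's figures; one-sided gives 7.82 and 10.46); stay of 1-3 hours; arrival difference D (intervention minus control) left after the self-report adjustment; slope b of Time 2 on true Time 1 eCO; reliability R of the Time 1 value given the self-report covariates; baseline SD 6.5-20 ppm.

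**1. The plan's figure.** SE = sqrt[2 × 900/(20 × 15) × (1 + 14r − 15h)].
- r = 0.10: sqrt(6 × 1.65) = 3.15; × 2.80 = 8.81 ppm.
- r = 0.30: sqrt(6 × 2.95) = 4.21; × 2.80 = 11.79 ppm.

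The stated 8.81 and 11.78 ppm are reproduced.

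**2. Washout slope.** b = 2^(−t/half-life). At 1, 2 and 3 hours this gives 0.79, 0.63, 0.50 (half-life 3 h) and 0.84, 0.71, 0.59 (half-life 4 h). The range is 0.50-0.84. The fitted slope could be near or above 1 if arrival level tracks how heavily people smoke.

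**3. Shift in the change-score contrast: (b − 1)D.** The sizes below are for b from 0.84 to 0.50.
- D = 2: 0.3-1.0 ppm, which is 4-11% of 8.81, 3-8% of 11.78, or about 0.1-0.3 SE at r = 0.10.
- D = 5: 0.8-2.5 ppm, which is 9-28% and 7-21%.

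If 795% is a ratio of means, mean arrival eCO is about 51.7/7.95 = 6.5 ppm. D = 2 is then 31% of the mean and D = 5 is 77%, which is large.

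**4. Shift with Time 1 eCO added: b(1 − R)D.** R must be conditional on the self-report covariates. For example, if marginal reliability is 0.80 and self-report explains half the true arrival variance, conditional R = 0.4/(0.4 + 0.2) = 0.67. For D = 5 ppm:

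| b | Change score | Adjusted, R = 0.80 | Adjusted, R = 0.67 | Adjusted less biased if R exceeds |
|---|---|---|---|---|
| 0.50 | −2.5 | +0.5 | +0.8 | any R |
| 0.71 | −1.5 | +0.7 | +1.2 | 0.59 |
| 0.84 | −0.8 | +0.8 | +1.4 | 0.81 |
| 1.00 | 0 | +1.0 | +1.7 | never |
| 1.20 | +1.0 | +1.2 | +2.0 | 0.83 |

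The last column is (2b − 1)/b for b < 1 and 1/b for b > 1. A null simulation (20 cafés, 15 per arm, r = 0.10, baseline SD 10, R = 0.8, D = 5, 2,000 runs, Monte Carlo SE 0.07) agreed. Change score / adjusted was −2.51 / +0.48 at b = 0.50, −0.71 / +0.92 at 0.84 and +0.05 / +1.06 at 1. This confirms the algebra and says nothing about the true b.

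**5. Averaging two readings.** With independent errors, marginal R rises from 0.80 to 1.6/1.8 = 0.89, and the conditional value in the example from 0.67 to 0.4/(0.4 + 0.1) = 0.80. At b = 1 and D = 5 the shift falls from 1.7 to 1.0 ppm. Error common to both readings is not reduced.

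**6. Precision.** With D = 0, adjustment removes q = (1 − bR)² × SD²/900 from the patron-level variance, and the SE factor is sqrt[(1.65 − q)/1.65] at r = 0.10.
- Largest gain (SD 20, b 0.50, R 0.8): q = 0.36 × 400/900 = 0.16, factor 0.950, so the SE is 5.0% lower. At r = 0.30, sqrt(2.79/2.95) = 0.973, or 2.7% lower.
- Smallest (SD 6.5, b 0.84, R 1): q = 0.001, no visible change.

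With D = 5 and SD 6.5, uncertainty in the slope adds 25 × 900 × 0.9/(600 × 42.25) = 0.80 to the variance of 9.9. The SE goes from 3.15 to 3.27, about 4% higher.

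**The case against.** The strongest reply is that, without randomised balance, change score against baseline adjustment is a known trade-off. The planned model is therefore a legitimate choice, and the protocol gives a reason for it. That stands as far as it goes. A reader might infer that the planned analysis is invalid, or that the adjusted model is always safer. The documents support neither: at b = 1 the change score carries no arrival bias and the adjusted model does, and at b = 0.84 the two tie or the adjusted model is worse, depending on R.

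The survey already covers hookah use and recent combustible products, which should be major sources of arrival CO, and the model adjusts for baseline tobacco use. Because eCO is itself described as a consumption marker, that phrase could be read to include it. This narrows the concern but shows that the phrase needs itemising.

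The eCO Form and interviewer scripts are listed in the Appendix but not reproduced, so a reading rule may exist there. Up to two samples could also mean a repeat only after a failed blow. Hence the claim is only that no rule is visible.

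A reader might also expect agreement between paired readings to show which model is less biased. It does not: it gives marginal reliability, an upper guide to the conditional value that matters.

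**Conclusion.** The point holds as a minor prespecification gap. Time 1 eCO is collected before exposure, is not named in the primary model, and has no visible rule for repeat readings, in a design where arrival eCO is not balanced by randomisation.

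The likely size is small: 0.3-1.0 ppm for D = 2 and 0.8-2.5 ppm for D = 5 over the washout slopes, and nothing if D = 0 or b = 1. For slopes of 0.50-0.71, adjustment reduces arrival bias at both reliabilities shown. With no systematic arrival difference it costs essentially nothing and lowers the SE by 0 to about 5%. D, b, R, baseline SD and length of stay are all assumptions.

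Three stronger inferences are not supported. The power figures are not undermined: 8.81 and 11.78 ppm stand. The two models do not always bracket the arrival effect: their shifts have opposite signs only when b < 1, and for b > 1 they err the same way. Adjustment also does not remove other confounding of arm with period from the fixed control-first order.

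**What to change.** In the Analytical Plan:

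- Name Time 1 eCO as an individual-level covariate in the primary hierarchical model, alongside itemised self-report covariates.
- Define the Time 1 value as the mean where two valid samples exist, otherwise the single valid sample. Use that same value in the change score and as the covariate; boost and Time 2 eCO as outcome then give the same arm estimate. State a parallel rule for Time 2.
- Prespecify the model without the covariate as a sensitivity analysis, and report both.
- Report mean arrival eCO by arm and the fitted slope. If agreement between paired readings is reported, describe it only as an upper guide to reliability.
- Use time in the café to describe washout, not as a covariate, because it follows exposure.

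The cost is one covariate and two reading rules in PROC MIXED, with no new data and no change in sample size. The statistical risk is added bias if a systematic arrival difference meets a slope near or above 1 and a baseline that is unreliable given self-report (about 1.0 ppm at conditional reliability 0.8 and 1.7 ppm at 0.67, for D = 5 and b = 1), and an SE up to about 4% higher at D = 5. That is why the unadjusted model should be shown beside it.
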